- To analyze the proportion of participants which achieve $\geq 50\%$ of dietary and exercise goals.
- To explore the effect of CEDI on ChT toxicity and post-op complications

Study design:

- Open label randomized controlled trial

Patient recruitment:

Recruitment will be conducted at the Oncology center of Hospital Beatriz Ângelo and patient selection will be done during the weekly multidisciplinary meeting. Patients will be enrolled at diagnosis of upper GI cancer, namely esophagus, gastric and pancreatic, provided that they are eligible for neoadjuvant ChT and with age higher than 18 years and lower than 80 years. Sample size per group was calculated bearing in mind that according to data from the World Health Organization, 14% of Portuguese adults are compliant to moderate exercise, and in our study adherence will be set as a compliance higher than 50%. Considering a power of 0.80 and an α set at 0.05, 25 patients will be needed per group. Stratified block randomization will be

conducted to allocate 25 patients to standard care and 25 to CEDI. Stratification will be performed according to disease location. Randomization will be undertaken by a randomization list created by a web based randomization system.

Methods:

- ***Clinical data:***

Demographic data such as age, sex, education level, drinking and smoking habits, and clinical data as tumor site and histological type, ChT regimens, response and toxicity, will be retrieved from electronic records. Adverse effects will also be recorded, namely ChT toxicity graded according to NCI Common Toxicity Criteria, and post -operative complications with Clavien Dindo classification.

- ***Patient Generated Subjective Global Assessment (PG-SGA)***

PG-SGA is known to be an accurate tool for the identification of malnourished cancer patients (Ottery F. , 1996) (Ottery F. , 1994). In our study, PG-SGA assessment will be conducted by an experienced dietitian and patients will be classified as well nourished (SGA A), moderately or suspected of being malnourished (SGA B) or severely malnourished (SGA C).

- ***Anthropometric measures (AM):***

AM have been used consistently due to their non-invasive feature, portability, and low cost (Rosa G, 2008). AM such as weight and height will be obtained, and Body Mass Index will be calculated. All AM will be conducted according to previously established protocols (Rosa G, 2008).

- ***Body composition assessment***

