Dietary intake will be assessed with a Food frequency questionnaire and 24 recalls using a modified USDA five-pass method at diagnosis and every visit until surgery. The Semi-quantitative Food Frequency Questionnaire that will be used, was developed for the Portuguese population (Lopes, Aro, Azevedo, Ramos, & Barros, 2007) and is designed to evaluate usual dietary intake. This questionnaire includes 86 commonly-eaten food or drinks and participants were asked to estimate the amount and frequency of intake of each food/drink according to frequency and amount. Conversion of foodstuffs to nutrients will be conducted with software Food Processor Plus (ESHA Research, Salem, Oregon) which has been adapted to the Portuguese commonly-eaten food or drinks.

The 24h recall using a modified USDA five-pass method consists in 5 steps, the first is to list all foods consumed on the previous 24h. On the second step the interviewer asks about possible forgotten food items. In the third step the interviewer clarifies the time and occasion of the consumed foods. On the fourth step subject answers to standardized questions and clarifies portion size. In the last fifth step the interviewer seeks to obtain any additional information related to the foods consumed (Johnson & K, 2002). Conversion of foodstuffs to nutrients will be conducted with Sanut software which has been developed for the Portuguese population.

- ***Functional status assessment***

Performance Status will be assessed with Eastern Cooperative Oncology Group Performance Status scale (Oken, et al., 1982). According to these criteria patients are classified from grade 0

(fully active) to grade 4 (bedridden). Prior to initiation of ChT and before surgery, data on oxygen-consumption, optimum aerobic heart rate and ECG-recordings as well as 6 min walk test will be conducted. Also, hand held dynamometer assessing grip strength will be obtained. .

- ***Physical activity***

Physical activity will be assessed with the International Physical Activity questionnaire (Craig, Marshall, Sjostrom, Bauman, Booth, & Ainsworth, 2003). This questionnaire has been validated in several countries including Portugal, and is known to be a valid and reliable tool. Participants will be categorized has having a low, moderate or high physical activity according to the frequency, duration and intensity of physical activity on the previous seven days.

- ***Patient Reported Outcome Measures(PROMs)***

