- ***Adherence Assessment***

The primary outcome will be intervention adherence, in which patients consenting to engage in the intervention protocol will be evaluated. As a secondary outcome, we will assess to what extent participants achieve their dietary and exercise goals. Participants will be considered as adherent if they have met $\geq 50\%$ of their diet and exercise goals on the week preceding ChT. Also, follow up rates will be recorded, as well as comments on burden and acceptability of the intervention. Dropout rates and reasons for leaving the study will also be recorded. Contamination of the control arm will also be analyzed. Patients will be contacted every week by phone call or interview to assess adherence.

Statistical analysis:

Statistical analysis will be conducted for the primary and secondary outcome with an intention to treat and per protocol approach, respectively. Continuous variables will be described as mean, median and range, while categorical variables will be expressed as frequency and percentage. Differences in mean continuous variables will be analyzed by t-test or Mann Whitney U test as appropriate, according to variable's adjustment to a normal distribution. Shapiro-Wilk test will be used to test normality. Pearson or Spearman correlation analysis will be performed as appropriate to assess the association between continuous variables. Chi square test of independence or Fisher exact test will be used to assess the association between categorical variables.

Ethics:

The study protocol has been approved by the Scientific and Ethics Committee of Hospital Beatriz Ângelo in Loures, Portugal. Informed consent will be obtained from every patient.

Clinical data will be prospectively collected from electronic charts, however data will be coded in order to maintain anonymity.

References:

Bruera, E., Strasser, F., Palmer, J., Willey, J., Calder, K., Amyotte, G., et al. (s.d.). Effect of Fish Oil on Appetite and Other Symptoms in Patients With Advanced Cancer and Anorexia/Cachexia: A Double-Blind, Placebo-Controlled Study. *Journal of Clinical Oncology*, 21(1), 129-134.

Chu, M. P., Lieffers, J., Ghosh, S., Belch, A., Chua, N. S., Fontaine, A., et al. (2017). Skeletal muscle density is an independent predictor of diffuse large B-cell lymphoma outcomes treated with rituximab-based chemoimmunotherapy. *Journal of Cachexia, Sarcopenia and Muscle*, 8(2), 298-304.

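### Continuous measures taken before chemotherapy and before surgery: the plan does not say whether or how baseline is used and leaves out the stratification factor, where a prespecified ANCOVA would cost little and usually gain precision

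*Combined protocol and SAP*

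**What the plan says.** - **Design** (Patient recruitment): stratified block randomisation, 25 patients per arm. "Stratification will be performed according to disease location".
- **Functional measures** (Functional status assessment): "Prior to initiation of ChT and before surgery, data on oxygen-consumption, optimum aerobic heart rate", together with ECG recordings, "as well as 6 min walk test will be conducted". These have one value before and one after the intervention period.
- **Diet** (Dietary Intake assessment): a food frequency questionnaire and 24-hour recalls, the latter "using a modified USDA five-pass method at diagnosis and every visit until surgery".
- **Analysis** (Statistical analysis): "Differences in mean continuous variables will be analyzed by t-test or Mann Whitney U test as appropriate". The choice between the two tests follows the data: "Shapiro-Wilk test will be used to test normality". The section mentions no final value, change score, covariate or stratum.
- **Analysis sets** (Statistical analysis): "Statistical analysis will be conducted for the primary and secondary outcome with an intention to treat and per protocol approach, respectively".
- **Outcome labels** (Adherence Assessment): adherence is primary. The named secondary outcome is goal attainment: "we will assess to what extent participants achieve their dietary and exercise goals". The functional and dietary measures carry no label.

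**The concern.** Two pieces of information that the trial will already hold have no stated role in the comparison of arms: the patient's own baseline value and the stratum used in the randomisation. With 25 patients per arm only large differences can be detected, so unused precision matters.

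The silence on final value versus change also has consequences. Which of the two is more precise depends on the baseline correlation, and the order reverses at 0.5. If the choice is made once data are in hand, it is an unplanned analytic choice.

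Leaving out location does not inflate the type I error. If location predicts the final value, an unadjusted test on final values after stratified randomisation is somewhat conservative.

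The concern covers only continuous measures with a planned baseline. Adherence, goal attainment, toxicity and complications are outside it, as are patient-reported outcomes, which are planned only at the end of chemotherapy.

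**Working it through.** **The plan's own figure.** The 25 per group (Patient recruitment) rests on a binary rate. Reading 14% and 50% as the two proportions, two-sided α 0.05 and power 0.80, the pooled formula gives

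n = [1.960·√(2·0.32·0.68) + 0.842·√(0.14·0.86 + 0.50·0.50)]² / 0.36² = (1.293 + 0.512)² / 0.1296 ≈ 25.1, rounded up to 26.

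The arcsine formula gives 24.3, rounded up to 25. The figure is reproduced closely and does not depend on how continuous measures are analysed.

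**Inputs.** From the documents: n = 25 per arm, α = 0.05 (taken as two-sided), power 0.80, three disease locations. Assumed, because the documents give nothing: baseline correlation r = 0.3, 0.5 or 0.7; equal SDs before and after; site split 8/9/8 per arm; and, as a sensitivity case, 20 per arm with pre-surgery data.

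**Formulas.** In units of the final-value variance, the variance per patient is
- final value: 1, with N − 2 df
- change score: 2(1 − r), with N − 2 df
- ANCOVA on baseline and location: (1 − r²)·[1 + 1/(N − 6)], with N − 5 df. The bracket allows for chance imbalance in baseline, and location is taken as balanced by the stratification.

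The standard error is √(2·variance/n). The detectable difference is the one at which the noncentral t gives 80% power.

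For example, at r = 0.5 and N = 50 the ANCOVA variance is 0.75 × (1 + 1/44) = 0.767, and the standard error is √(2 × 0.767/25) = 0.248 SD.

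**Detectable difference (SD) at 80% power**

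| Analysis | n per arm | r = 0.3 | r = 0.5 | r = 0.7 |
|---|---|---|---|---|
| Final value | 25 | 0.81 | 0.81 | 0.81 |
| Change | 25 | 0.96 | 0.81 | 0.63 |
| ANCOVA | 25 | 0.78 | 0.71 | 0.58 |
| Final value | 20 | 0.91 | 0.91 | 0.91 |
| Change | 20 | 1.08 | 0.91 | 0.70 |
| ANCOVA | 20 | 0.88 | 0.80 | 0.66 |

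**Equivalent sample size.** To detect what ANCOVA detects with 25 per arm, a t-test on final values needs about 27, 32 and 47 per arm. At r = 0.7 a t-test on change needs about 28.5 per arm, so 47 applies only if final values are compared.

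**Power for a 0.6 SD effect, 25 per arm, location not prognostic.** Final values about 55%; change 42/55/76%; ANCOVA 58/66/82%. At 20 per arm: about 46%; 34/45/67%; 48/56/72%.

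**Contribution of location.** With baseline already in the model and site means 0.35 SD apart, simulation shows that adding location raises power by 2.9, 1.4, 0.7 and 0.1 points at r = 0, 0.3, 0.5 and 0.7. The t-test on final values then has a true size of 4.1–4.3%; simulated ANCOVA size is 4.7–5.2%. Nearly all the gain comes from baseline.

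**Cost if nothing is prognostic.** Power falls from 54.7% to 53.6% at 25 per arm and from 45.7% to 44.5% at 20 per arm.

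**Skewed data.** Simulated power with lognormal outcomes (log-scale SD 1) and an effect of 0.6 SD on the log scale, 25 per arm:

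| Analysis | r = 0 | r = 0.3 | r = 0.5 | r = 0.7 |
|---|---|---|---|---|
| Mann-Whitney, final value | 52% | 52% | 52% | 52% |
| ANCOVA, raw scale | 37% | 40% | 44% | 57% |
| ANCOVA, ranks | 52% | 56% | 62% | 77% |
| ANCOVA, log scale | 54% | 58% | 66% | 82% |

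The gain therefore depends on the scale being right.

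**The case against.** The strongest case against has four parts.

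1. **No stated aim depends on these measures.** The aims are adherence, completion, goal attainment, and exploratory toxicity and complications. The functional and dietary measures appear only under Methods. This stands, and it limits the point to minor.
2. **The gain depends on an unknown correlation and on the comparator.** At r = 0.3 it is only 0.81 to 0.78 SD, and at r of about 0.15 there is none. If location is treated as an ordinary randomly imbalanced covariate, with no credit for stratification, the ANCOVA figures become 0.80/0.73/0.60 and break-even rises to about r = 0.25. The 47 per arm shrinks to 28.5 if the team would have analysed change. All of this is correct. But nobody knows r in advance, ANCOVA beats both alternatives at all three correlations, and the loss at r = 0 is about one point of power.
3. **Location adds almost nothing once baseline is in the model.** Largely true. The reasons to include it are that the analysis then reflects the randomisation and that the test regains its nominal size.
4. **The remedy needs more detail.** The documents do not show which measures will be skewed, diet has two instruments and repeated visits, and control-arm visits are not defined. Optimum aerobic heart rate follows the same schedule as the other functional measures. These are fair drafting points and are taken up in the fix. None removes the case for baseline adjustment.

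**Conclusion.** The concern holds, as a minor point of efficiency and prespecification. The plan leaves the use of baseline open rather than excluding it, and its tests omit the stratification factor. The planned tests remain valid.

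At 25 per arm, ANCOVA lowers the detectable difference from 0.81 SD (final values) to 0.78, 0.71 or 0.58 SD at assumed correlations of 0.3, 0.5 or 0.7. Against the better of the two unadjusted analyses at each correlation, it is worth about 2, 7 and 3.5 patients per arm (26.7, 32.2 and 28.5 against 25). The benefit is negligible at low correlation, and with strong skew it requires a log or rank scale.

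The correlations, site split, site effects and skewness are all assumptions. The conclusion is confined to continuous measures with a pre-chemotherapy value.

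**What to change.** In the Statistical analysis section:

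- For oxygen consumption, the 6-minute walk and dietary intake, specify ANCOVA of the final value with the baseline value and disease location as covariates. Report the adjusted difference with a 95% CI. Optimum aerobic heart rate can be added, since it is measured at the same two times.
- For dietary intake, name the instrument and the final time point, and state at which visits control patients are assessed.
- Fix the scale for each measure in advance instead of by Shapiro-Wilk. Use the log scale for measures expected to be skewed, reported as an adjusted ratio with a 95% CI, or ANCOVA on ranks if only a test is wanted.
- Compare patients by randomised arm among all those with a final value. Covariate adjustment does not restore the randomised comparison in a per-protocol set.
- Keep the unadjusted t-test or Mann-Whitney test as a sensitivity analysis.

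Binary outcomes, patient-reported outcomes, the primary outcome and the sample size need no change.

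**Cost:** wording only, with no new visits or measurements, provided dietary recalls are collected in both arms as the Dietary Intake section implies. The statistical cost is about one point of power if neither covariate is prognostic. The one real risk is raw-scale ANCOVA on strongly skewed data, which choosing the scale in advance avoids.
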